## Study Protocol

### Participants

A total of  $N = 58$  Mexican students in grades 1-5 across eight public elementary schools in Sinaloa, Mexico participated in the current study ( $M = 7.25$  students/school, range = 6-8). For each student, one parent and one teacher were designated as “primary” (meaning they would participate in CLS-FUERTE and implement the strategies) and asked to complete all measures. All data was collected at the students’ respective schools. See Table 2 for demographic information and Figure 1 for participant flow.

**Recruitment.** Recruitment occurred between May and September each year and began with invitations to school principals suggested by the local SEP. As described in the introduction, as part of our augmented outreach/recruitment plan for Mexico, we invited all families and personnel in participating schools to an informational gathering in September in which we showed a silent video depicting a child with attention and impulse-control difficulties (i.e., the Behavioral Impairment Video; Haack, Gerdes, Lawton, & Schneider, 2014). We encouraged families to contact us if interested in a program to help children similar to the child in the video. School personnel also identified candidate children and contacted families about participating. See Figure 1 for recruitment flow and number of students deemed ineligible at each step of recruitment.

**Screening.** Interested parents scheduled an appointment to screen for eligibility. If parents attended the screening appointment, reported willingness/ability to participate in sessions, and described at least six youth symptoms of inattention and/or hyperactivity with at least one area of related impairment (i.e., school, family, or social impairment), we scheduled meetings for baseline assessments.

**Baseline Assessment.** After completing informed consent procedures approved by UCSF Committee on Human Research, parents and teachers of successfully screened students completed questionnaires, including the Child Symptom Inventory (CSI-4; Gadow & Sprafkin, 1997), Impairment Rating Scale (IRS; Fabiano et al., 2006), and demographic/history form. Students meeting the following criteria were eligible to participate: (a) at least six CSI-4 inattention symptoms and/or six

hyperactive/impulsive symptoms endorsed by parent or teacher as occurring often or very often, (b) at least one area of IRS functioning rated as  $\geq 3$  by both parent and teacher, thereby indicating cross-setting impairment, (c) a parent available to participate; and (d) a primary teacher agreeing to participate. The assessment and screening algorithm based on at least six symptoms per domain reported by parents or teachers has been used in previous school-based ADHD trials (Haack et al., 2018; Pfiffner et al., 2016) and is associated with strong predictive validity for ADHD (sensitivity = .80, specificity = .58; Gadow & Sprafkin, 2002) and ODD (sensitivity = .70, specificity = .90; Gadow & Sprafkin, 2002) diagnoses. Students taking medication were eligible as long as regimens were stable. Students with significant visual or hearing impairments, severe language delay, psychosis, or pervasive developmental disorder or who were in full-day special classrooms were excluded. Eligible students provided assent before participating.

### **Study Design**

A 2-level (students, schools) cluster RCT design (Hayes & Moulton, 2009) accounted for treatment (CLS-FUERTE or BAU) within level 2 (schools). We randomized schools to CLS-FUERTE (school n = 4, student n = 28) or BAU (school n = 4, student n = 31). We determined our sample size based on practical considerations (i.e., previous CLS trial experience, years of funding). Each year, schools were divided into high or low Socioeconomic Status (SES) categories (determined by the Secretary of Public Education; SEP) after baseline assessments were completed in September. The first author coded schools to conceal their identity until treatment was assigned and a statistician randomized concealed ordered pairs to CLS-FUERTE or BAU using a random number generator. Those randomized to CLS-FUERTE received the intervention between October and December, followed by post assessments for all families in December each year.

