### **Data Analytic Approach**

We performed all statistical analyses using SPSS (Version 26; IBM Corp, 2019). We analyzed outcomes in three domains (i.e., ADHD and ODD symptoms, and overall impairment) separately for each rater (i.e., parent and teacher). Primary analyses involved generalized estimating equations (GEE) using the SPSS GENLIN procedure with unstructured correlation matrices to examine within (baseline; post-treatment) and between (CLS-FUERTE vs BAU) group comparisons, adjusting for school clustering. GEE was chosen over alternative methods due to relaxed distribution requirements. Analyses were completed initially without covariates. We then performed follow-up analyses adjusting for parental level of education and child age, gender, and ADHD medication status; however, inclusion did not change the pattern or interpretation of results. Therefore, simple analyses without covariates are presented. To control

for Type 1 Error, a Benjamini-Hochberg false discovery rate (FDR; Benjamini & Hochberg, 1995) was applied within domain. The FDR exerts a more powerful control over wrongly rejecting the null compared to other procedures that control for family-wise error (e.g., Bonferroni correction). For all pairwise comparisons, Hedges'  $g$  effect size metrics are provided. Hedges'  $g$  estimates are Cohen's  $d$  estimates corrected for the upward bias associated with smaller sample sizes. Interpretation of Hedges'  $g$  estimates are consistent with traditional effect size conventions (i.e., 0.2 = small; 0.5 = moderate; 0.8 = large).

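### With 8 randomised schools, the GEE mentions no small-sample correction of the standard error and no t reference; an uncorrected school-level test would reject a true null about 14% of the time

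*Combined protocol and SAP*

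**What the plan says.** **Design.** The Study Design section gives the allocation as "We randomized schools to CLS-FUERTE (school n = 4, student n = 28) or BAU (school n = 4, student n = 31" students. Each year "schools were divided into high or low Socioeconomic Status (SES) categories", and then "a statistician randomized concealed ordered pairs to CLS-FUERTE or BAU using a random number generator". The term ordered pairs is not defined. Pairing within SES category is the natural reading, because the SES split has no other stated purpose, but the text does not say so.

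**Analysis.** The Data Analytic Approach specifies "generalized estimating equations (GEE) using the SPSS GENLIN procedure with unstructured correlation matrices", used "to examine within (baseline; post-treatment) and between (CLS-FUERTE vs BAU) group comparisons, adjusting for school clustering". It does not say whether the school or the student is the GEE subject, which type of standard error is used, or which reference distribution gives the p-value. It also does not say whether the arms are compared on change or at post-treatment.

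**Covariates.** The first model has none. The follow-up model is described as "adjusting for parental level of education and child age, gender, and ADHD medication status". The section states that "inclusion did not change the pattern or interpretation of results" and concludes: "Therefore, simple analyses without covariates are presented". Neither model names school SES, pair or year.

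**Multiplicity and small samples.** A Benjamini-Hochberg step is applied within each domain. The only small-sample correction mentioned is Hedges' g, which concerns the effect size and not the standard error or the test.

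**The concern.** The sandwich variance is justified by a large number of clusters, and here there are eight. It is built from residuals around fitted arm means, so with four schools per arm it is too small on average. It is also very noisy, and a normal reference takes no account of that noise. Both effects make p-values too small.

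Six comparisons are at stake: three domains, each for two raters. The false discovery rate procedure takes the p-values as given, so it passes any inflation through.

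The SES split is a second and smaller matter. If schools were paired within SES and SES predicts the analysed contrast, a model without SES counts SES variation as noise that the design has already balanced. That pushes the test in the conservative direction. The question is whether this offsets the small-sample inflation.

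**Working it through.** **Inputs from the documents.** There are 8 schools, 4 per arm, with 58 students and a mean of 7.25 per school (range 6-8). The mean reproduces: 58/8 = 7.25. The arm counts in Study Design give 28 + 31 = 59, not 58. Using 59 changes the power figures below by about 1 point at most.

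**Assumptions.** The documents give no SD, ICC or SES gap. I take school as the GEE subject, the contrast SD as 1, the between-school variance vb as 0.02 or 0.05, two-sided 5%, and a true effect of 0.8 SD for power. Pairs are formed within SES, two pairs per SES category unless stated. Paired figures below are for vb = 0.02/0.05.

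**Step 1: no SES effect.** The variance of a school mean is v = vb + (1 - vb)/7.25, which is 0.155/0.181. The true SE of the arm difference is sqrt(2v/4) = 0.279/0.301. With four equal schools per arm the uncorrected sandwich variance averages 3/4 of the true variance, so on the root-variance scale the SE is sqrt(0.75) = 0.87 of its true value. The size of the z test is 2 x P(t on 6 df > 1.960 x 0.866) = 14.1%. With a corrected SE and t on 6 df (critical value 2.447) the size is 5.0%.

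**Step 2: SES gap between categories, model without SES.** Simulated type I error, 100,000 trials per scenario, 58 students:

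| SES gap (SD) | Uncorrected SE, z | Corrected SE, t on 6 df |
|---|---|---|
| 0 | 14.1/14.2% | 5.0/5.0% |
| 0.2 | 12.7/13.0% | 4.4/4.4% |
| 0.3 | 11.3/11.6% | 3.7/3.9% |
| 0.5 | 7.6/8.6% | 2.1/2.4% |

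With a 3:1 split of pairs the uncorrected z test is at 8.4/9.2% at a gap of 0.5. In a check with equal clusters, the uncorrected test comes down to 5% only at a gap of about 0.65-0.70 SD (2:2) or 0.75-0.80 SD (3:1).

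SE bias and test size are different questions. For the 2:2 split the mean sandwich variance divided by the true variance is 0.75 + gap²/(4v). It equals 1 at gap = sqrt(v) = 0.39/0.43. At a gap of 0.5 the variance is therefore too large on average, yet the test still rejects too often because of the few degrees of freedom.

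**Step 3: SES added.** With the uncorrected SE and z, the size is 18.1-18.4%. With the corrected SE and t on 5 df (critical value 2.571) it is 5.0-5.1% for the 2:2 split and 5.2-5.4% for 3:1.

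**Step 4: what SES adjustment buys once the SE is corrected.** Power without SES is 67/61% at gap 0, 64/58% at 0.2, 60/54% at 0.3 and 48/45% at 0.5. With SES it is about 63/57% throughout. The closed-form break-even gap is sqrt(6v((2.571/2.447)² - 1)/2). For vb = 0.02 this is sqrt(6 x 0.155 x 0.104/2) = 0.22, and for vb = 0.05 it is 0.24. For a 3:1 split the values are 0.25/0.27.

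**Step 5: student as GEE subject.** School correlation is then ignored. The design effect is 1 + (7.25 - 1) x ICC, and the size is 2 x P(Z > 1.960/sqrt(design effect)). This gives 5.7%, 8.7%, 12.4% and 19.1% at assumed ICCs of 0.01, 0.05, 0.10 and 0.20. This reading cannot be ruled out. An unstructured matrix over two time points within a student is one correlation. Over a school's 12-16 observations it would be 66-120 correlations to estimate from 8 schools.

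**The case against.** **A correction may have been used and not described.** This stands. The documents show only that none is mentioned, and the 14% is conditional on the uncorrected form with school as subject.

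**The calculation is a school-mean contrast, not the GEE itself.** Also true. The problem comes from having four schools per arm, so the contrast captures it, but the figures are indicative.

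**A reader might infer that the direction of error is unknown, because leaving out SES and leaving out the correction pull in opposite directions.** The documents do not support this. The low figures of about 2% belong to a corrected test and the 14% to an uncorrected one, so together they are not a range for one analysis. The uncorrected test stays above 5% at every gap from 0 to 0.5 SD. Only strong pairing reverses this. In terms of correlation between paired school means, the crossing is at about 0.55-0.6, and nothing in the documents suggests a value that high.

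**A reader might infer that omitting SES makes the analysis invalid.** It does not. With a corrected SE the omission only makes the test conservative. If pairs were not formed within SES, the corrected unadjusted test stays at about 5%. For a comparison of change, an SES difference in level alone cancels. The follow-up model with parental education, a partial proxy for SES, left the results unchanged. That is some evidence against a large gap, although it is not the SEP school category.

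**Conclusion.** The point holds as a minor one, and it is about small-sample inference rather than about SES. With 8 schools, a school-level sandwich SE with a z test has a size of about 14% at a nominal 5%. It falls to about 8-9% at an SES gap of 0.5 SD and to 5% only near 0.7 SD (two pairs per SES category). Within the plausible range the test is anti-conservative.

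This rests on school being the GEE subject, an uncorrected SE, a normal reference, and the assumed school variances. If the student is the subject, the size depends on an ICC that the documents do not give. These are per-test figures, not error rates after the false discovery rate step. They do not show that any particular result is a false positive.

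**What to change.** 1. **Main change.** Keep the existing model with school as the clustering unit. For each of the six outcomes, say whether the contrast is group-by-time or post-treatment. Report it with a small-sample-corrected cluster-robust SE and a t reference on 8 - 2 = 6 school-level df, and apply the false discovery rate step to those p-values. State the GEE subject, the SE type and the reference distribution.
2. **Secondary.** State whether pairs were formed within SES category and year. If they were formed within SES, report alongside a corrected analysis with SES category and SES x time on 5 df, labelled as added later. It gains power only above a gap of about 0.2-0.3 SD.
3. **Avoid.** Do not add SES to an uncorrected z test.

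**Cost.** There is one re-analysis per outcome, plus one more if the SES analysis is run, using a school variable already recorded. The corrected SE may need a procedure other than the GENLIN call described. Compared with an uncorrected z interval, equal clusters give intervals wider by a factor of (2.447/1.960) x sqrt(4/3) = 1.44. The SES analysis costs one further df. If SES does not predict the contrast, its intervals are about 4% wider (1.362 against 1.309 at vb = 0.02) and about 3 points of power are lost.

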### **Intervention: CLS-FUERTE**

The CLS-FUERTE program is a comprehensive psychosocial treatment for school-aged youth (grades 1-5) delivered by Mexican School Mental Health Professionals (SMHPs) directly at the students' school site. The six-week program encompasses weekly parent management training groups led by the SMHP, weekly student skills groups led by the SMHP, and daily classroom management by the teacher

supported by the SMHP. The program is designed to teach parents, students, and teachers a common language encouraging skill use to address impairment related to ADHD and ODD. Thus, students in CLS-FUERTE receive around-the-clock prompting and reinforcement for goal behaviors related to school, family, and social functioning.

**Parent component.** Parents attended six 90-minute groups teaching strategies to manage attention/behavior challenges including positive consequences (e.g., rewards, praise), negative consequences (e.g., planned ignoring, removing privileges), and routines. Each group, SMHPs reviewed and troubleshooted strategies assigned and presented new strategies. Parents also reviewed skills covered in the student group and were taught methods to promote and reinforce skill generalization. Groups were held at school sites and scheduled to accommodate participating families, often after drop-off.

**Child component.** Students attended six 60-minute groups teaching strategies to compensate for attention/behavioral challenges, including organization (e.g., routines) and social skills (e.g., good sportsmanship, handling teasing). SMHPs targeted skill knowledge and implementation through didactic instruction, modeling, behavioral rehearsal via interactive games, corrective feedback, and in-vivo practice via role plays. Students received reinforcement (i.e., praise, tickets called “stars”, small prizes) for following rules, participating in activities, and practicing skills. Self-management of alertness was targeted with group-reinforced attention checks (Pelham Jr. & Hoza, 1996). To encourage skill generalization, students brought in “stars” they earned at home and class to exchange for praise and a group-based reward (i.e., celebratory party). Groups occurred during the school day at students’ respective schools; groups were scheduled by the SMHPs based on the collective input they received from participating teachers regarding the most suitable day and time for children to attend group, usually during a nonacademic period.

**Classroom component.** Teachers attended a 60-minute orientation, during which SMHPs provided an overview of attention/behavior concerns and the use of a school–home daily report card (DRC). Teachers selected two or three behavior goals tailored for each student, which were discussed with the parent and student during a 15 to 30-minute meeting. Behavior goals could include academic

targets (e.g., gets started on work right away, completes work accurately) or social-emotional targets (e.g., keeps hands/feet to self, asks for help when needed). Teachers rated each behavior up to three times per school day on a 3-point scale (0= goal not met, 1=needs improvement, 2=goal met). Students were prompted to bring their DRC home daily to exchange points for rewards. Skills taught in the student groups were shared with teachers to promote cross-setting reinforcement and generalization.

**SMHP Training, consultation, and fidelity monitoring.** SMHPs in the Sinaloa school district have bachelor's or master's degrees in education but are not consistently required to receive training or observation in EBTs (Sanchez-Sosa, 2007; Stark et al., 2010). Typically, they are assigned caseloads of students with mental health disorders (approximately 20 students per caseload with a maximum of 25 students). SMHPs are provided a manual which contains information for educating youth with mental health disorders but lacks presentation of any specific strategies (*The New Mexican School*, 2019). We recruited SMHPs in the current study via their school principals. Each SMHP was assigned a member of our team as their primary trainer. To enhance consistency in training and feedback, each SMHP's primary trainer led (or co-led) their initial training and consultation meetings, as well as attended each session.

Each participating SMHP attended an initial 8-hour training with their trainer to learn psychoeducation about attention/behavior challenges and the principles supporting psychosocial ADHD/ODD intervention (such as structuring antecedents and providing reinforcement to encourage goal behaviors), learn and practice behavior management strategies to employ during meetings and groups (e.g., attention checks, differential reinforcement), as well as learn and practice the first meetings of each component (i.e., the first parent group, the first student group, the teacher orientation and the teacher-family-student DRC meeting). Each week during the program, SMHPs attended 60-90 minute consultation meetings with their trainer to review upcoming manual content, role-play key content, and troubleshoot problems. SMHPs were provided a detailed, scripted manual for each component. In the initial training and weekly consultation meetings, trainers modeled intervention delivery, presented video clips of previous SMHPs delivering the intervention, and guided SMHPs in role-playing the intervention delivery.

Each parent, child, and classroom component session was led by SMHPs with in-vivo observation from their trainer to rate fidelity/engagement and answer questions or provide modeling of the curriculum as needed. Specifically, trainers monitored how much of the scripted manual content SMHPs delivered in each session, as well as the quality of SMHP delivery, including clarity in presenting each skill, effectiveness in responding to questions, use of group management strategies to maintain balance of participant involvement and enhance engagement, and use of time management strategies. Trainers also rated each participant's attendance and engagement in the session. Trainers provided prompting or modeling as needed to ensure accurate delivery of content, improve group implementation quality, and/or enhance participant engagement. Fidelity ratings were reviewed in weekly consultation meetings and strategies were discussed and practiced as needed to improve SMHP fidelity and participant engagement in future meetings.

**BAU Condition.** Those assigned to BAU received school services as usual. These services typically included tutoring with SMHPs. Of note, those in CLS-FUERTE also continued to receive school services as usual throughout the intervention period. After post assessments were completed (which occurred at the same time in both treatment conditions), BAU families were invited to receive CLS-FUERTE and BAU SMHPs were trained to implement the program.

### **Data Analytic Approach**

We performed all statistical analyses using SPSS (Version 26; IBM Corp, 2019). We analyzed outcomes in three domains (i.e., ADHD and ODD symptoms, and overall impairment) separately for each rater (i.e., parent and teacher). Primary analyses involved generalized estimating equations (GEE) using the SPSS GENLIN procedure with unstructured correlation matrices to examine within (baseline; post-treatment) and between (CLS-FUERTE vs BAU) group comparisons, adjusting for school clustering. GEE was chosen over alternative methods due to relaxed distribution requirements. Analyses were completed initially without covariates. We then performed follow-up analyses adjusting for parental level of education and child age, gender, and ADHD medication status; however, inclusion did not change the pattern or interpretation of results. Therefore, simple analyses without covariates are presented. To control

for Type 1 Error, a Benjamini-Hochberg false discovery rate (FDR; Benjamini & Hochberg, 1995) was applied within domain. The FDR exerts a more powerful control over wrongly rejecting the null compared to other procedures that control for family-wise error (e.g., Bonferroni correction). For all pairwise comparisons, Hedges'  $g$  effect size metrics are provided. Hedges'  $g$  estimates are Cohen's  $d$  estimates corrected for the upward bias associated with smaller sample sizes. Interpretation of Hedges'  $g$  estimates are consistent with traditional effect size conventions (i.e., 0.2 = small; 0.5 = moderate; 0.8 = large).

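### The primary GEE pairs an unstructured correlation matrix with adjustment for school clustering but does not name the GEE subject, and neither natural choice of subject delivers both

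*Combined protocol and SAP*

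**What the plan says.** The Study Design section describes "A 2-level (students, schools) cluster RCT design", with four schools randomised to each arm. The Participants section reports 58 students "across eight public elementary schools in Sinaloa, Mexico participated in the current study", a mean of 7.25 "students/school, range = 6-8". On sample size, Study Design says: "We determined our sample size based on practical considerations". No ICC, power or effect size is given.

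The Data Analytic Approach section covers three outcome domains, each analysed separately for parent and teacher ratings, which makes six primary models with two scores per student in each. The model is a GEE, described as follows: "SPSS GENLIN procedure with unstructured correlation matrices to examine within (baseline; post-treatment) and between (CLS-FUERTE vs BAU) group comparisons, adjusting for school clustering". That sentence is all the section says about clustering. It does not state the GEE subject, how school enters the model, which covariance estimator was used, or any degrees of freedom or small-sample correction for eight schools.

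**The concern.** The data have three levels: two occasions within a student, students within a school, and eight schools. A GEE has one subject level and one working correlation matrix. An unstructured matrix is natural for the two occasions within a student. Adjustment for school requires the robust variance to be summed over schools. The sentence claims both properties, and the subject decides which of them can hold.

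Every between-arm standard error and p-value comes from these models. If school is absent from the variance and changes are correlated within school, p-values are too small. Such correlation is plausible, because each school's groups are led by its own mental health professional, with an assigned trainer attending every session. The Benjamini-Hochberg procedure acts on the p-values after that and cannot repair them.

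**Working it through.** **Inputs.** 8 schools, 4 per arm (Study Design); 58 students, 6 to 8 per school (Participants); 2 occasions, raters analysed separately (Data Analytic Approach). The plan's cluster size reproduces: 58/8 = 7.25. The arm counts in Study Design sum to 28 + 31 = 59, not 58. This does not affect the argument; the simulations used 58 students split 28/30 or 27/31.

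**School as subject.** A school with n students gives k = 2n responses, and an unstructured matrix has k(k − 1)/2 correlations:

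- n = 6: k = 12, 12 × 11/2 = 66
- n = 7: k = 14, 14 × 13/2 = 91
- n = 8: k = 16, 16 × 15/2 = 120

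These would be estimated from 8 schools. The raw moment matrix has rank at most 8. With the diagonal set to 1, as in a working correlation, it regains full rank but is indefinite. With eight schools of 8 students, the 16 × 16 estimate was not positive definite in 500 of 500 simulated trials; with a mix of 7- and 8-student schools, in 498 of 500. Moreover, student 1 in one school does not correspond to student 1 in another, so a correlation between positions 1 and 2 has no common meaning.

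**Student as subject (or student within school).** k = 2, so there is 2 × 1/2 = 1 correlation, which is easily estimated. The robust variance then treats all students as independent.

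**Student as subject with school as a fixed factor.** Arm is constant within school, so arm and school are aliased. School main effects cancel from the arm-by-time contrast, but school-by-time variation, which belongs in its error, is still omitted.

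**Size if student was the subject.** Assumptions: complete data, normal change scores, two-sided 5%, no gain from pairing. The ICC is that of the change score. The design effect is DE = 1 + (7.25 − 1) × ICC, the standard error is too small by a factor √DE, and the approximate type I error is P(|Z| > 1.96/√DE). For example, at ICC 0.10, DE = 1 + 6.25 × 0.10 = 1.625, √DE = 1.275, and P(|Z| > 1.537) = 12.4%.

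| ICC | DE | √DE | Student as subject, analytic | Student as subject, simulated | School-robust, normal critical value, simulated | t-test on 8 school mean changes, simulated |
|---|---|---|---|---|---|---|
| 0 | 1.000 | 1.00 | 5.0% | 5.7% | 14.3% | 5.2% |
| 0.02 | 1.125 | 1.06 | 6.5% | 7.7% | 14.4% | 4.9% |
| 0.05 | 1.3125 | 1.15 | 8.7% | 10.2% | 14.0% | 4.8% |
| 0.10 | 1.625 | 1.27 | 12.4% | 14.4% | 14.3% | 4.7% |
| 0.20 | 2.250 | 1.50 | 19.1% | 21.7% | 13.9% | 5.0% |

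The student column used 40,000 trials per ICC. The last two columns used 8,000 each with the 28/30 split and an independence working matrix; the 27/31 split gave 13.3% to 14.2% and 4.7% to 5.1%.

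**Check of the correction.** With K = 8 schools and p = 2 parameters (intercept and arm), the scaling is K/(K − p) = 8/6. With equal school sizes, the uncorrected robust variance contributes Σe²/16 per arm, where e is a school's deviation from its arm mean. The usual variance of a mean of four is Σe²/(4 × 3) = Σe²/12. The ratio is 16/12 = 8/6, so the scaled test on 6 df is then the school-level t-test. With 6 to 8 students per school and the independence matrix, its simulated type I error was 4.8% to 5.4%.

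**The case against.** The strongest reply is that the text shows an omission, not a failure. The section is written after the analyses were done and reports that adding covariates did not change the results, so some model was fitted. An unstructured matrix with school as subject would hardly fit, so it is probably not what was reported. This stands: the documents do not show which version was run, and the failure of the school-level matrix does not measure the error in the reported results. But naming the subject would not be enough, since each natural choice leaves one of the two stated properties unmet.

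A second reply is that a sandwich standard error does not need a correct working correlation. That is true when school is the subject and the working matrix can be estimated and inverted, as with an independent or exchangeable matrix. It does not rescue the unstructured matrix, nor the analysis with student as subject.

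A third is that eight school means per occasion could be analysed with a 2 × 2 unstructured matrix and school as subject. That would be coherent, but the follow-up models adjust for child age, gender and medication, which points to student-level rows.

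A fourth is that harm depends on the ICC of change, and stable school differences cancel from change. This stands. At ICC 0 the error is about 6%, and that small excess comes from the normal reference, not from clustering. Study Design also mentions SES categories and ordered pairs, and the calculation credits no gain from them.

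**Conclusion.** The concern holds. As written, the primary model cannot be both unstructured and adjusted for school under either natural choice of subject, so the specification must change as well as its description. The correlation counts depend only on the plan's own figures. The type I errors of about 6%, 8%, 10%, 14% and 22% apply only if student was the subject, and rest on the assumed ICCs and the conditions listed with the calculation.

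A reader might infer four stronger things that the documents do not support:

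- **That the reported p-values are known to be too small, or the efficacy findings false.** Neither the subject nor the ICC is given.
- **That the school-level matrix fails because it is singular with rank at most 8.** That describes the raw moment matrix. With a unit diagonal the estimate is full rank but indefinite.
- **That small-sample corrections cannot help because they invert the working matrix.** Not all do: the 8/6 scaling and the school-level t-test need no such inverse.
- **That making school the subject is enough.** With normal critical values it gives about 14% type I error at every ICC tried, worse than student as subject up to ICC 0.05 and about equal at 0.10.

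**What to change.** State the GENLIN subject and covariance estimator that were used. Re-specify the six primary models so that school is the cluster and the inference is valid for eight clusters, by one of these routes:

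- One change score (post minus baseline) per student, school as subject, an independent or exchangeable working correlation, the robust variance scaled by 8/6, and a t reference on 6 df. The simulated error rate above was obtained with the independent matrix.
- A t-test on the eight school mean changes with 6 df: the same test when school sizes are equal, and close to it here.
- A mixed model with an unstructured 2 × 2 residual for time within student, random school and school-by-time effects, and small-sample degrees of freedom.

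If the reported between-arm standard errors and p-values came from student as subject, replace them, and reapply the false discovery rate procedure to the new p-values. The cost is new syntax, a rerun of six models on existing data, and wider intervals.
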